### **9.2 Complete Response**

Any RECIL assessments determined to be a CR will be confirmed by no morphologic, immunohistochemical, or flow cytometric evidence of disease by BM biopsy or aspirate (Brugger et al 2004).

### **9.3 Minimal Residual Disease**

Minimal residual disease (MRD) is defined as the minimal traceable persistence of lymphoma after treatment with acalabrutinib. The clonoSEQ® assay, developed by Adaptive Biotechnologies, is an NGS-based immunosequencing platform that will be used for the detection, quantification and analysis of MRD. The assay uses multiplex PCR, high throughput sequencing and a proprietary algorithm for evaluating lymphoid clonal distribution and expansions in genomic DNA. MRD positive or negative results will be determined by detection

of residual clonal cells (with assay sensitivity of  $10^{-6}$ ) per Adaptive Technologies' reporting methods.

An MRD status will be defined as all results from whole blood and BM that meet the assay testing requirements and are negative for the presence of residual clonal cells. An MRD+ status will be defined as all results from whole blood or BM that are positive for residual clonal cells per Adaptive Biotechnologies' reporting methods. In addition to MRD positivity or negativity, MRD level will be captured by recording the number of residual clonal cells detected.

## **10. STATISTICAL CONSIDERATIONS**

### **10.1 Statistical Design**

This is a Phase II, single arm, multi-center trial designed to assess the safety and efficacy of acalabrutinib as maintenance therapy post-BMT in subjects with MCL. The primary objective of this trial is to determine the percentage of subjects who receive at least one dose of acalabrutinib and who are alive and free of PD or relapse at 2 years post-BMT.

### **10.2 Sample Size Considerations**

The primary endpoint is the percentage of patients who are alive and free of PD or relapse at 2 years post-BMT. A sample size of 45 patients produces a two-sided 95% CI of 65%-90% when the observed percentage is 80%. To account for a 10% non-evaluable rate, the total sample size will be 50 patients.

### **10.3 Analysis Population**

The following analysis populations will be used:

- The Safety Analysis Set is defined as all patients who receive at least one dose of acalabrutinib.
- The Efficacy Analysis Set is defined as all patients who receive at least one dose of acalabrutinib, who have an adequate baseline disease assessment and an adequate post-baseline assessment, and those who discontinue due to death or PD prior to their first assessment.

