## **2. STUDY OBJECTIVES**

### **2.1 Primary Objective**

The primary objective of this study is to:

- Determine the PFS rate of subjects who received at least one dose of acalabrutinib and are alive and free of PD or relapse 2 years post-BMT.

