## **9. RESPONSE EVALUATIONS AND MEASUREMENTS**

### **9.1 Progression-free Survival**

Progression-free survival is defined as the time from Day 0 of BMT until the date of objective radiological PD according to RECIL or death (by any cause in the absence of PD). Patients who are alive and free from PD will be censored at the date of last tumor assessment. Patients who begin subsequent therapy prior to PD or death will be censored at the date of last tumor assessment prior to the start of subsequent therapy.

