### **10.4 Data Analysis**

Descriptive statistics, including mean, median, standard deviation, and range for all continuous measures, will be tabulated and reported. Percentages and frequencies for all categorical measures will also be presented. Time-to-event endpoints will be reported using Kaplan-Meier estimates, with 95% CIs for median time to event. A full description of the analysis will be included in the Statistical Analysis Plan.

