#### **10.4.2 Efficacy Analysis**

All efficacy analyses will be performed using the Efficacy Analysis Set.

- PFS is defined as the time from Day 0 of BMT to objective radiological PD or death on study. PFS will be evaluated as Kaplan-Meier estimates of the percentage of subjects who receive at least one dose of study drug and who are alive and free of PD or relapse at 2 years post-BMT according to RECIL (Younes et al 2017). Data for subjects who are still alive and free from progression at the time of data cut-off date, are lost to follow-up, have discontinued the study, or have initiated a subsequent protocol therapy will be censored on last assessment (or, if no post-baseline tumor assessment, at the time of first dose plus 1 day). Approximate 95% CI for median duration of PFS will be computed using the formula proposed by Brookmeyer and Crowley.
- Minimal residual disease status will be examined by NGS on all bone marrow aspirate and blood samples collected up to 2 years post-BMT to determine the conversion rate from MRD+ to MRD while taking acalabrutinib, correlate MRD status with PFS, and identify mutations that correlate with disease relapse. An MRD status will be defined as all results from whole blood and BM that are negative for the presence of residual clonal cells (with assay sensitivity of 10^-6). An MRD+ status will be defined as all results from whole blood or BM that are positive for residual clonal cells per Adaptive Biotechnologies' reporting methods.

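### The primary objective covers every subject with at least one dose, but PFS is analysed in a narrower set that can drop treated patients with countable events

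*Combined protocol and SAP*

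**What the plan says.** Section 2.1 gives this primary objective: "PFS rate of subjects who received at least one dose of acalabrutinib and are alive and free of PD". The time point is 2 years after transplant, and relapse counts alongside progression. Section 10.1 repeats the aim in similar terms: "determine the percentage of subjects who receive at least one dose of acalabrutinib and who are alive and free of PD or relapse". The PFS bullet in Section 10.4.2 again describes the Kaplan-Meier percentage among subjects with at least one dose.

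Section 10.4.2 opens, however, with "All efficacy analyses will be performed using the Efficacy Analysis Set". Section 10.3 defines that set as dosed patients "who have an adequate baseline disease assessment and an adequate post-baseline assessment, and those who discontinue due to death or PD" before their first assessment. The population that the objective names does exist in 10.3, but only as the Safety Analysis Set.

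Three other rules bear on this:

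- Section 9.1 counts objective radiological progression or death from any cause as an event, with time running from the day of transplant. On other treatment it says "Patients who begin subsequent therapy prior to PD or death will be censored at the date of last tumor assessment" before that therapy began.
- Section 10.4.2 censors at the last assessment or, "if no post-baseline tumor assessment, at the time of first dose plus 1 day".
- Section 10.2 sizes the study on 45 patients and adds: "To account for a 10% non-evaluable rate, the total sample size will be 50 patients". It does not define non-evaluable.

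Section 10.4 defers detail: "A full description of the analysis will be included in the Statistical Analysis Plan". The document as supplied contains no separate SAP text that settles the matter.

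**The concern.** Membership of the Efficacy Analysis Set depends on what happens after first dose, and partly on outcome. An unscanned patient who discontinues for death or progression stays in; an unscanned patient who leaves for toxicity or withdrawal does not. Neither an adequate assessment nor discontinuing (of drug, or of the study) is defined in 10.3, so some patients could be placed either way once the data are known.

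This is a single-arm study of about 50 patients, and the 2-year rate is its main result. If the denominator is not fixed by first dose, the reported rate may describe a different group from the one in the objective, and an event that 9.1 would count may never enter the analysis. The rule censoring unscanned patients the day after first dose also fits an all-treated set; 10.3 leaves few patients to whom it could apply.

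**Working it through.** **1. The plan's own figures.** The inputs, from Section 10.2, are n = 45, an observed 80% (36/45) and a 10% non-evaluable rate. The exact (Clopper-Pearson) 95% interval for 36/45 is 65.4% to 90.4%, which matches the 65%-90% in 10.2. The total is 45/0.9 = 50. Both reproduce. (The Synopsis prints 65%-95%; that is a separate inconsistency.)

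**2. Who is dropped.** Sections 9.1, 10.3 and 10.4.2 set side by side for treated patients:

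| Treated patient | In the 10.3 set? | PFS contribution under 9.1 and 10.4.2 |
|---|---|---|
| Adequate baseline and adequate post-baseline assessment | Yes | Event or censoring as usual |
| Discontinues for death or progression before first assessment | Yes | Death, or radiological progression, is an event |
| Never scanned after baseline, no event recorded | No | Would be censored at first dose plus 1 day |
| Inadequate baseline, later progression or death | No, once past the first assessment | Event lost |
| Stops drug for another reason, never scanned, no other therapy, then dies | No, if discontinuing refers to drug | Event lost |

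The last two rows are where a countable event disappears. An inadequate baseline is not far-fetched. Section 6.5.14 asks for imaging within 28 days before first dose, while Appendix D allows the scan from Day 80 (footnote s) and a Cycle 1 start up to Day 120 (footnote c). The largest gap is 120 - 80 = 40 days. Whether such a baseline is adequate is not stated, and those passages need reconciling.

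**3. Effect on Kaplan-Meier.** This is an illustration, not a forecast. Take 45 patients in the set, 9 events by 24 months, 36 event-free and no earlier censoring. The product telescopes to 36/45 = 80.0%, with standard error √(0.8 × 0.2/45) = 0.0596, about 6.0 points. Now restore excluded patients, assuming first dose on Day 100:

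- *Five restored, all censored at Day 101, before any event:* they leave the risk set before it matters. The estimate stays 36/45 = 80.0%, SE 6.0. If one of the nine events fell before Day 101, it would be (49/50) × (36/44) = 80.2%.
- *One restored with a recorded event after Day 101:* 36/46 = 78.3%, SE √(0.783 × 0.217/46) = 6.1 points; a fall of 1.7.
- *Two such patients:* 36/47 = 76.6%; a further fall of 1.7.
- *One restored with an inadequate baseline but followed event-free to 24 months:* (36 + 1)/(45 + 1) = 80.4%; a rise of 0.4.

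Other restored patients who are only censored at Day 101 do not alter these figures.

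**The case against.** The case for leaving the plan alone has real force.

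- *Most restored patients change nothing.* An unscanned patient without an event is censored the day after first dose, so adding that patient leaves the estimate where it was. This stands.
- *The rule already protects against the obvious bias.* A patient with radiological progression has by definition been scanned, and early death or progression is kept by the exception. This stands too, and confines the problem to the last two rows of the table.
- *The evaluable set is prespecified and the study was sized on it.* True, but the objective is stated three times for a different population, and 10.4.2 contains both versions.
- *The SAP may resolve it.* Possibly. The protocol text would still conflict, and the sensitivity analysis below is conditional on what the SAP already contains.

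A reader might infer more: that with 5 of 50 excluded, a reported 80% is compatible with anything from 36/50 = 72% to 41/50 = 82% among treated patients. The documents do not support that range. It needs five treated patients who all fall in the narrow cases above and all share one outcome. The upper end cannot arise from unscanned patients, who would be censored. The 10% in 10.2 is undefined and may include people never dosed, since consent generally precedes transplant and second screening follows at Day 80 to 100 (Section 5).

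A reader might also infer that everyone who stops drug before the 6-month scan is dropped. That depends on whether the 6-, 12-, 18- and 24-month scans continue off drug. Sections 5 and 6.4 and Appendix D footnotes f and s suggest they do. Sections 6.4.5 and 6.4.6 list no imaging, and the scan marks in Appendix D end with the maintenance columns. This is a separate ambiguity.

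**Conclusion.** The mismatch is real: the objective names all treated subjects, and the analysis uses a subset that can discard events the PFS definition counts. Nothing else in the document repairs it.

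The likely size is small and may be nil. The number excluded is not given. Each restored patient with a recorded event would lower the estimate by about 1.7 points on the 36/45 base, under a third of the standard error. This assumes no other early censoring and an event after Day 101. The net direction is unknown, and the documents do not show that the planned analysis inflates the rate. The point is worth acting on because the correction is nearly free and fixes the denominator before the data are seen.

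**What to change.** 1. In Sections 10.3 and 10.4.2, make all patients with at least one dose (the existing Safety Analysis Set) the primary PFS set, under the event and censoring rules already in 9.1 and 10.4.2. Keep the Efficacy Analysis Set as supportive, and define for it what an adequate assessment is and whether discontinuing means drug or study.
2. Unless the SAP already does so, add a sensitivity analysis that counts treated patients without 24-month status as failures. Patients censored earlier for subsequent therapy fall in this group, so report how many there are. This is needed because item 1 alone does not move Kaplan-Meier for patients who are simply censored the day after first dose.
3. Separately, reconcile Sections 5, 6.4, 6.4.5 and 6.4.6 with Appendix D on whether the scheduled scans continue after drug is stopped.

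Items 1 and 2 cost protocol and SAP wording and one extra table, with no new data collection. The downside is a possibly slightly less favourable primary figure.

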### **10.4 Data Analysis**

Descriptive statistics, including mean, median, standard deviation, and range for all continuous measures, will be tabulated and reported. Percentages and frequencies for all categorical measures will also be presented. Time-to-event endpoints will be reported using Kaplan-Meier estimates, with 95% CIs for median time to event. A full description of the analysis will be included in the Statistical Analysis Plan.

#### **10.4.1 Demographics and Baseline Characteristics**

Demographic and baseline disease characteristics will be summarized using descriptive statistics. Data to be tabulated will include demographic features such as age, sex, and race, as well as disease-specific characteristics.

The number and percentages of patients enrolled, treated, completed the treatment/study and withdrawn from treatment/study for any reason will be presented.

#### **10.4.2 Efficacy Analysis**

All efficacy analyses will be performed using the Efficacy Analysis Set.

- PFS is defined as the time from Day 0 of BMT to objective radiological PD or death on study. PFS will be evaluated as Kaplan-Meier estimates of the percentage of subjects who receive at least one dose of study drug and who are alive and free of PD or relapse at 2 years post-BMT according to RECIL (Younes et al 2017). Data for subjects who are still alive and free from progression at the time of data cut-off date, are lost to follow-up, have discontinued the study, or have initiated a subsequent protocol therapy will be censored on last assessment (or, if no post-baseline tumor assessment, at the time of first dose plus 1 day). Approximate 95% CI for median duration of PFS will be computed using the formula proposed by Brookmeyer and Crowley.
- Minimal residual disease status will be examined by NGS on all bone marrow aspirate and blood samples collected up to 2 years post-BMT to determine the conversion rate from MRD+ to MRD while taking acalabrutinib, correlate MRD status with PFS, and identify mutations that correlate with disease relapse. An MRD status will be defined as all results from whole blood and BM that are negative for the presence of residual clonal cells (with assay sensitivity of 10^-6). An MRD+ status will be defined as all results from whole blood or BM that are positive for residual clonal cells per Adaptive Biotechnologies' reporting methods.

#### **10.4.3 Safety Analysis**

Safety will be assessed through the analysis of the reported incidence of treatment-emergent AEs. Treatment-emergent AEs are those with an onset on or after the initiation of therapy, and will be graded according to NCI CTCAE Version 5.0. A copy of the CTCAE scoring system may be downloaded from:

[https://ctep.cancer.gov/protocolDevelopment/electronic\\_applications/docs/CTCAE\\_v5\\_Quick\\_Reference\\_8.5x11.pdf](https://ctep.cancer.gov/protocolDevelopment/electronic_applications/docs/CTCAE_v5_Quick_Reference_8.5x11.pdf).

The AEs will be coded using the Medical Dictionary for Regulatory Activities (MedDRA) and summarized using system organ class and preferred term for all patients in the Safety Analysis Set. In addition, summaries of SAEs, AEs leading to treatment discontinuation, AEs by maximum NCI CTCAE grade, and AEs related to the study drug will also be presented.

Other safety endpoints including laboratory results, vital signs, ECG findings, and other protocol-specified tests will be listed and/or summarized for all patients in the Safety Analysis Set.

Concomitant medications will be coded using the WHO Drug Dictionary and they will be listed and summarized.

#### **10.5 Analysis Time Points**

##### **10.5.1 Final Analysis**

The final analysis of the study will occur following the last visit of the last patient.

## 11. SAFETY REPORTING AND ANALYSES

Safety assessments will consist of monitoring and recording protocol-defined AEs and SAEs, and measurement of protocol-specified hematology, clinical chemistry, and urinalysis variables, and measurement of protocol-specified vital signs.

The PI is responsible for recognizing and reporting SAEs to the Innovations Safety Department (Section 11.1.5). It is Innovations' responsibility to report relevant SAEs to the applicable local, national, or international regulatory bodies. In addition, Investigators must report SAEs and follow-up information to their responsible IRBs according to the policies of each IRB.

The PI is also responsible for ensuring that every staff member involved in the study is familiar with the content of this section.

### 11.1 Definitions

#### 11.1.1 Adverse Events

Adverse event means any untoward medical occurrence associated with the use of a drug in humans, whether or not considered drug-related. An AE can be any unfavorable and unintended sign (e.g., an abnormal laboratory finding), symptom, or disease temporarily associated with the use of a drug, without any judgment about causality. An AE can arise with any use of the drug (e.g., off-label use, use in combination with another drug) and with any route of administration, formulation, or dose, including overdose.

#### 11.1.2 Serious Adverse Events

An AE or a suspected adverse reaction (SAR) is considered “serious” if it results in any of the following outcomes:

- **Death**
- **A life-threatening AE**
- **Inpatient hospitalization of at least 24 hours or prolongation of existing hospitalization**
- **A persistent or significant incapacity or substantial disruption of the ability to conduct normal life functions**
- **A congenital anomaly/birth defect**
- **Important medical events that may not result in death, be life-threatening, or require hospitalization may be considered serious when, based upon appropriate medical judgment, they may jeopardize the patient and may require medical or surgical intervention to prevent one of the outcomes listed in this definition.**

Examples of such medical events include:

- **allergic bronchospasm requiring intensive treatment in an emergency room or at home,**
- **blood dyscrasias or convulsions that do not result in hospitalization, or**
- **development of drug dependency or drug abuse.**

It is important to distinguish between “serious” and “severe” AEs, as the terms are not synonymous. Severity is a measure of intensity; however, an AE of severe intensity need not necessarily be considered “serious.” Seriousness serves as the guide for defining regulatory reporting obligations and is based on patient/event outcome or action usually associated with events that pose a threat to a patient’s life or vital functions. For example, nausea which persists for several hours may be considered “severe” nausea, but may not be considered an SAE. On the other hand, a stroke which results in only a limited degree of disability may be considered only a mild stroke, but would be considered an SAE. “Severity” and “seriousness” should be independently assessed when recording AEs on the eCRF and SAEs on the SAE Report Form.

### **11.1.3 Adverse Reaction**

An adverse reaction (AR) means any AE caused by a drug. Adverse reactions are a subset of all SARs where there is a reason to conclude that the drug caused the event.

### **11.1.4 Suspected Adverse Reaction**

Suspected adverse reaction means any AE for which there is a reasonable possibility that the drug caused the AE. “Reasonable possibility” means that there is evidence to suggest a causal relationship between the drug and the AE. An SAR implies a lesser degree of certainty about causality than an AR, which means any AE caused by a drug.

### **11.1.5 Adverse Events of Special Interest**

The following events are adverse events of special interest (AESIs) for subjects exposed to acalabrutinib, and must be reported to the sponsors expeditiously (see Section 11.1.6.2 for reporting instructions), irrespective of regulatory seriousness criteria or causality.

- Ventricular arrhythmias (e.g., ventricular extrasystoles, ventricular tachycardia, ventricular arrhythmia, ventricular fibrillation, etc.).

### **11.1.6 Recording and Reporting of Adverse Events**

#### **11.1.6.1 Recording of Adverse Events**

All AEs of any patient during the course of the research study will be recorded in the eCRF, and the Investigator will give his or her opinion as to the relationship of the AE to the study drug (e.g., whether the event is related or unrelated to study drug administration).

All AEs should be documented. A description of the event, including its date of onset and resolution, whether it constitutes an SAE or not, any action taken (e.g., changes to study drug), and outcome should be provided along with the Investigator’s assessment of causality (e.g., the relationship to the study drug). For an AE to be a suspected TEAE there should be at least a reasonable possibility of a causal relationship between the protocol treatment and the AE. Adverse events will be graded according to the NCI CTCAE Version 5.0, and changes will be documented.

If the AE is serious, it should be reported immediately to the Innovations Safety Department. Other untoward events occurring in the framework of a clinical study are to be recorded as AEs (e.g., AEs that occur prior to assignment of the study drug that are related to a protocol-mandated intervention, including invasive procedures such as biopsies, medication washout, or no treatment run-in).

Any clinically significant signs and symptoms, abnormal test findings, changes in physical examination, hypersensitivity, and other measurements that occur will be reported as AEs and collected on the relevant eCRF screen.

Test findings will be reported as an AE if: the test result requires an adjustment in the study drug(s) or discontinuation of treatment; test findings require additional testing or surgical intervention; a test result or finding is associated with accompanying symptoms; and/or a test result is considered to be an AE by the Investigator.

